4.1 Study Protocol

4.1.a. Overview. All patients will undergo study testing at baseline prior to initiating treatment with the GF-IGB system, ESG, or MRP. Study testing will consist of two separate visits within 7 days of each other at both baseline and at 10% total body weight loss (TBWL). On visit one, patients will undergo a gastric emptying study and on visit two, patients will undergo a mixed meal test and VAS for hunger. All subjects will be called weekly to review weight loss and rate of weight loss in order to appropriately time end study testing.

4.1.b. Treatments (Standard of Care): The three groups will consist of patients undergoing the following clinical treatments as part of their clinical care. These treatments are not affected by study participation.

GF-IGB System Treatment: After the patients meet all clinical GF-IGB system treatment (FDA approved, Appendix B) criteria and pre-placement activities, patients report to the endoscopy lab after an overnight fast for balloon administration at their own expense. The balloon, contained in a hard, cellulose food grade capsule and attached to a thin catheter, is swallowed by the patient in a standing position. Once the two-step verification of balloon passage into the stomach by both fluoroscopy and pressure reading, the balloon is inflated to a volume of 250 ml with a nitrogen-mix gas, additional imaging of the inflated balloon is obtained, the catheter is ejected from the balloon, and the catheter is pulled out through the patient's mouth. The process is repeated at week 2 for the second balloon and between weeks 4-8 for the third balloon based on patient preference. All patients are given an individualized calorie prescription by a registered dietitian for a goal of up to 2 pounds of weight loss per week. The balloons are removed endoscopically 6 months after placement of the first balloon(5). Patients also attend monthly virtual individual diet coaching and monthly virtual group behavior coaching sessions both delivered by a registered dietitian for twelve months focused on long-term behavior change, 6 months while the balloons are in place and six months after the balloons are removed.

ESG Treatment: After the patients meet all clinical ESG treatment criteria, patients report to the endoscopy lab after an overnight fast for the ESG procedure at their own expense. Endoscopic sleeve gastroplasty is a weight loss procedure that uses an FDA 510K cleared endoscopic suturing device known as Overstitch to reduce the size of the gastric body. The procedure is completed with an endoscope, which is a flexible tube with a camera, with the suturing device attached at the distal tip. suturing device attached to it. It is inserted through the mouth, down the esophagus, and into the stomach. Sutures with 8-10 bites 1.5-2 cm apart in a U-shape pattern are placed starting distally 6 cm proximal to the pylorus. When the suture is tightened the greater curve of the stomach is reduced in size. Additional sutures are placed moving proximally up to 2 cm distal to the gastroesophageal junction. An additional row of sutures is then placed again in the distal to proximal stomach to complete the gastroplasty. The final shape of the gastric body is a tube 3-4 cm in diameter. This decreases the amount of food one can consume, which leads to the consumption of fewer calories throughout the day, resulting in weight loss. However, for long-term success and maintenance of weight loss, a healthy diet and exercise are also required with the consumption of smaller portion sizes. All patients are given an individualized calorie prescription by a registered dietitian for a goal of up to 2 pounds of weight loss per week. Patients also attend monthly virtual individual diet coaching and monthly virtual group behavior coaching sessions both delivered by a registered dietitian for twelve months focused on long-term behavior change.

MRP: After patients meet all criteria for the medically supervised MRP program and enroll in the program at their own expense, patients are given an individualized calorie prescription by a registered dietitian for a goal of 2 pounds weight loss per week. Patients are seen in a group-based program once a week focused on long-term behavior change and use meal replacements for a nutritionally balanced very low-calorie diet for 20 weeks.

4.1.c. Gastric emptying study (research related). After an overnight fast, patients will report to the radiology suite at the University of Colorado Hospital. Subjects will consume a meal consisting of 118 ml (4 oz) of liquid egg substitute mixed with technetium colloidal sulfur and cooked until firm, two pieces of white bread, and 29 gm of a jam as well as 120 ml of water ingested upright over 10 minutes. Immediately after ingestion, planar static imaging of the anterior and posterior abdomen with the patient in the upright position will be performed. Radiotracer activity in the stomach will be obtained with anterior and posterior regions of interest placed over the stomach, and percent retention calculated using the geometric mean at baseline, 0.5 hour, 1 hour, 2 hours, 3 hours, and 4hours after ingestion. If there is less than 10% food remaining in the stomach at the 3 hour mark the gastric emptying study will stop at 3 hours.

4.1.d. Mixed Meal Test (research related): On a day separate from the gastric emptying study, patients will report to the Clinical Translational Research Center (CTRC) at the University of Colorado School of Medicine after an overnight fast. An intravenous catheter will be inserted into a hand or forearm vein for blood draws. Immediately before and at 15, 30, 60, 90, 120, 150, and 180 minutes after consumptions of a mixed meal, blood will be drawn for measurement of acyl-ghrelin, plasma insulin, and plasma glucose concentrations. The mixed meal will be a mixture of liquids and solids and contain 550 kcal with a macronutrient content of 51% carbohydrate, 33% fat, and 16% protein.

4.1.e. Visual Analogue Scales to assess Hunger (Research Related): A validated questionnaire (The Visual Analogue Scales for measurement of appetite sensations) ²⁶ will be given to patients during the mixed meal test. Subjects will fill out the questionnaire immediately before the mixed meal and at 15, 30, 60, 90, 120, 150, and 180 minutes after consuming the mixed meal.

4.1.f. Follow-up weight at 12 months: patients will report for a follow-up visit at 12 months after initiating therapy for weight.

5. Statistical Analysis.

5.1 Data analysis. The primary analysis will be a group by study-time repeated (baseline-end study) measures analysis of variance which will include an evaluation of statistical contrasts that compare between group differences in changes from baseline to end. Analyses will be performed on the following variables: percent of gastric retention at 2 hours, fasting and Area Under the Curve (AUC) for acyl ghrelin, insulin, glucose, and VAS-hunger. A Student's t-test for paired samples will also be performed on each variable from baseline to end-study testing. All data will be analyzed using SPSS (IBM, Armonk, NY)

5.2 Power calculation. The primary endpoints used for the power calculation in this study are change in gastric emptying at 2 hours, acyl-ghrelin concentrations, and visual analog scale. In assessing statistical power, we will use statistical contrasts of change from baseline between the groups, assuming 11 patients in each group. Based on previous work, a conservative estimate of standard deviation of the change is assumed to be roughly 80% of the amount of change for fasting acyl-ghrelin and VAS Hunger (16) and 60% for percent gastric retention at 2 hours ¹¹. All tests are two-sided and performed at the 0.05 level of significance. GPower 3.1 (Universitat Duesseldorf, Germany) was used for power calculations. The impact of these assumptions is as follows (Table 1):

Table 1. Power Calculations

Variable	Baseline	Response to Weight Loss			Between Group (compared with MRP)	
		MRP	GF-IGB	ESG	GF-IGB	ESG
% Retention at 2 hours	25±14.5%	0	+12.5 (50%)	+12.5 (50%)	96%	96%
Acyl Ghrelin pg/ml	125±100	+50 (40%)	+10 (8%)	+10 (8%)	86%	86%
Visual Analog Scale	32±25	+11 (40%)	0	0	80%	80%

6.0. Study timeline.

Subjects will be recruited over two years from patient populations already at the University of Colorado. Our current practice had 15 GF-IGB patients per year since the start of the program with 80% of the current patient population meeting study criteria. Our current practice also had 18 ESG patients in the last 12 year months with 75% of the current patient population meeting study criteria. The MRP at the University of Colorado enrolls >40 patients per year with >50% meeting study inclusion criteria. Baseline to End-Study Testing is expected to take 16 weeks per patient. Consenting will need to be performed on 25 subjects in each group (total of 75 subjects). Assuming an attrition rate of 20% for patients undergoing baseline testing, all study testing should be completed with 11 subjects in each group within two years. If a participant has not reached 10% TBWL by the end of the clinic program, they will be withdrawn from the study.

7.0 Recruitment and Consenting:

Study participants in the GF-IGB and ESG group will be recruited from the endoscopic bariatric therapy clinical practice who have passed all clinical pre-procedure testing and are scheduled to undergo device placement. Study participants in the MRP group will be recruited from the My New Weigh meal replacement program who have met all clinical program entry criteria. Medical records will be reviewed for inclusion and exclusion criteria prior to consent and subjects will be asked face to face, or over the phone if they would like to participate in this study. Patients will then be scheduled for consent and screening. The consenting process will be performed by the study coordinator in a face to

face visit. Only the study participant will be allowed to provide consent for the study.

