4.1 Subjects: The study population will consist of 11 patients with a BMI 30-40 kg/m² and age 22-65 years old who are weight stable (defined as <5% weight change in the last 3 months) and initiating clinical treatment with the GF-IGB system, 11 patients with a BMI 30-40 kg/m² and age 22-65 years old who are weight stable (defined as <5% weight change in the last 3 months) and initiating clinical treatment with ESG, and 11 patients with a BMI 30-40 kg/m² and age 22-65 who are weight stable and initiating clinical treatment with a medically supervised MRP (My New Weigh; University of Colorado, Anschutz Health and Wellness Center). After undergoing any required laboratory testing or imaging for the patient's self-chosen treatments, patient will present for screening. The screening visit will consist of a history and physical examination, the Patient Health Questionnaire- 9 (PHQ-9)²⁴, and the Questionnaire on Eating and Weight Patterns – 5²⁵ (Appendix A). Patients with a history of liver disease, uncontrolled thyroid disease, anemia, diabetes, eating disorder, uncontrolled depression defined as a score ≥ 10 PHQ-9, on weight loss medications in the last 3 months, history of gastroparesis, bariatric surgery, or history to allergy or intolerance to any component of the meal used in the gastric emptying study or mixed meal test will be excluded. Women who are pregnant or lactating, prisoners, non-English speakers, and decisionally challenged adults will also be excluded. We anticipate consenting 25 patients in each arm to achieve the required number of patients completing all study testing in each arm for achieve adequate statistical power (See 5.2 Power Calculation). We will attempt to match enrollment based on BMI in categories of BMI 30-34.9 kg/m² and 35-40 kg/m².

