8.4 Gastric Emptying Study: This research involves exposure to radiation equivalent to 40 mrems per study from the gastric emptying study. This is equivalent to <13%% of the amount of average radiation exposure adults in the US receive each year. Participants could also have an allergic reaction to the food components of the test. All subjects will be advised of the radiation exposure and will be questioned about food allergies and if they have a known allergy to any component of the test meal, they will be excluded from the study.

8.5 Intravenous catheter insertion: Possible side effects of intravenous catheter insertion are discomfort, bruising, and/or bleeding at the site of needle insertion. Occasionally some people experience dizziness or feel faint. An infection can occur at the site of catheter insertion. Aseptic technique for intravenous catheter insertion will be used to prevent infection, participants will have IV catheter insertion while seated or reclined, and the site will be monitored during the mixed meal test for any signs of intravenous catheter malfunction.

9.0 Data Monitoring:

This the study related procedures in this protocol (questionnaires, visual analog scale, gastric emptying study, and mixed meal tests with blood draws) are low risk. The PI will review any adverse events that occur from study related procedures as they occur. There will not be a formal interim analysis.

10.0 Potential Scientific Problems:

This is an ambitious protocol which will require enough patient volume for adequate enrollment, however we have adequate patient populations to recruit for this study. Detailed follow-up of patients is necessary to ensure testing at 10% TBWL, and I have experience with two other trials that required carefully monitoring weight to eliminate confounding from change in weight. I will employ similar strategies in this study to test patients at the required %TBWL and we have budgeted for an assumed 20% attrition rate after enrollment and baseline testing to have adequate sample to achieve sufficient

power.

11.0 Funding:

Grant funding is currently pending for this study from the American Society for Gastrointestinal Endoscopy, but PI start-up funds are currently available to complete all study testing.

References

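### Table 1's 86% power for acyl-ghrelin does not follow from the SD rule that reproduces its other two rows; one common SD gives about 80% or 61%

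*Combined protocol and SAP*

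**What the plan says.** Section 5.2 names three primary endpoints for the power calculation: change in gastric retention at 2 hours, acyl-ghrelin and VAS hunger. For the comparison, "we will use statistical contrasts of change from baseline between the groups, assuming 11 patients in each group". On the error rate, "All tests are two-sided and performed at the 0.05 level of significance".

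The spread comes from a proportional rule. It is described as "a conservative estimate of standard deviation of the change", and the "standard deviation of the change is assumed to be roughly 80% of the amount of change for fasting acyl-ghrelin and VAS Hunger"; for retention the proportion is 60%. The text does not say whether the percentage applies to each arm's own change, to the larger change or to the difference between arms. It also does not say whether the two arms share one SD.

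Table 1 then gives, for each device against MRP:

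| Row | Baseline | MRP change | Device change | Printed power |
|---|---|---|---|---|
| Retention at 2 h (%) | 25 ± 14.5 | 0 | +12.5 | 96% |
| "Acyl Ghrelin pg/ml" | 125 ± 100 | +50 | +10 | 86% |
| VAS hunger | 32 ± 25 | +11 | 0 | 80% |

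Section 4.1 (Subjects) ties the number consented to completing enough patients "for achieve adequate statistical power". Section 10.0 says attrition has been budgeted for "to have adequate sample to achieve sufficient" power.

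**The concern.** Ghrelin and VAS share one sentence, one percentage and one sample size, yet their printed powers differ by 6 points. If the SD is 80% of the difference between arms, both rows have the same standardised effect, 1/0.8 = 1.25, and must have the same power. If it is 80% of the MRP change, ghrelin must come out below VAS, because its difference (40) is smaller than the MRP change (50). With one SD common to both arms, neither reading puts ghrelin above VAS.

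What is at stake is how a null ghrelin result will be read. A power of 86% means a 14% chance of missing the assumed effect. That chance is about 20% with SD 32 and 39% with SD 40.

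**Working it through.** **Inputs.** All come from section 5.2 and Table 1: 11 per arm, two-sided 0.05, contrast of change from baseline, SD rule 80% / 80% / 60%, and the changes tabulated above. I assume the two-sample *t* calculation from the noncentral *t* distribution, as GPower would do it.

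**Formula.** d = difference in mean change / SD of change; df = 20; noncentrality = d × √(11/2) = 2.345 d; critical value 2.086.

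**Step 1: reproduce the rows that work, with one common SD.**
- Retention: SD = 0.60 × 12.5 = 7.5; d = 12.5/7.5 = 1.667; power 96.0% (printed 96%).
- VAS: SD = 0.80 × 11 = 8.8; d = 11/8.8 = 1.25; power 79.6% (printed 80%).

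One arm has zero change in each of these rows, so the changing arm's change equals the difference. The rows show that a common SD was used. They cannot show which change the percentage refers to.

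**Step 2: apply the same rule to ghrelin.** The difference is 50 − 10 = 40.
- SD = 0.80 × 40 = 32: d = 1.25; power 79.6%.
- SD = 0.80 × 50 = 40: d = 1.00; power 60.7%.
- Printed: 86%.

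**Step 3: can rounding explain it?** VAS prints as 80% for fractions from 0.791 to 0.801. Over that range ghrelin is 79.5–80.5% (difference-based), 60.6–61.7% (MRP-based) or 87.0–87.8% (each arm's own change). None of these rounds to 86%.

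**Step 4: can a three-arm error term explain it?** With df = 30, retention is 96.6%, VAS 81.0%, and ghrelin 81.0% (SD 32) or 62.2% (SD 40). Ghrelin is still short of 86%, and the other two rows no longer match.

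**Step 5: arm-specific SDs.** Taking 80% of each arm's own change gives 40 (MRP) and 8 (device). The root mean square is √((40² + 8²)/2) = 28.8; d = 40/28.8 = 1.387; power 87.1%. Taken literally in the other rows, this convention gives SD 0 in the no-change arm, and power rises to 99.9% for retention (7.5 and 0) and 97.6% for VAS (8.8 and 0).

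**Step 6: what 86% requires.** Powers of 85.5% to 86.5% correspond to d = 1.353 to 1.373. This means either:
- a common SD of 29.6 to 29.1, which is 74% to 73% of the difference (at 73.4%, VAS would also be 86%); or
- MRP at 40 and a device-arm SD of about 12 to 10.

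**Step 7: is so small a device SD conservative?** If the ± values in Table 1 are baseline SDs (an assumption), an SD of change requires a baseline-to-end correlation of at least √(1 − (SD of change / baseline SD)²). For ghrelin, 8/100 requires 0.997 and 11/100 requires 0.994. The plan's own SDs require 0.936 for VAS (8.8/25) and 0.856 for retention (7.5/14.5).

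**Step 8: detectable difference.** Power of 80% at 11 per arm needs d = 1.256, which is 1.256 × 32 = 40.2 pg/ml or 1.256 × 40 = 50.2 pg/ml, against 40 assumed. The second figure is the whole assumed MRP rise.

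**The case against.** The strongest defence is that the planner did use arm-specific SDs. A percentage-of-change rule gives no usable SD where the assumed change is zero, so the planner may have borrowed the other arm's SD there. That gives 96.0%, 87.1% and 79.6% against the printed 96%, 86% and 80%: two rows match and ghrelin is about one point off. Since the text says only roughly 80%, a fraction of 81% for ghrelin alone gives 86.3%; SDs of 40 and 10 give 86.4%. On this view the 86% is an undisclosed assumption and not a miscalculation.

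This is a plausible account of where the number came from, and it is why 86% should not simply be struck out. But it needs three things the plan does not state: unequal SDs, a borrowed SD for arms with no change, and a separate rounding for ghrelin. At the stated 80% it still gives 87.1%.

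Three further points limit the finding.
- The 61% figure depends on an SD of 40 in the device arm, four times that arm's assumed change of 10. It is one branch, not the established answer.
- The ± values are 80% (100/125), 78% (25/32) and 58% (14.5/25) of the baseline means, close to the plan's 80/80/60 proportions. They may not be observed SDs, so the correlation argument is supporting evidence only.
- This is a pilot study, and nothing here changes the number of patients.

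**Conclusion.** The concern holds. The common SD behind the retention and VAS rows gives 79.6% or 60.7% for ghrelin, against 86% printed: an overstatement of 6 or 25 points. The document cannot settle which applies. With SD 32 the consequence is modest, since ghrelin then has the same power the plan already accepts for VAS. With SD 40, 11 per arm falls well short of 80% power for the assumed 40 pg/ml difference, and the adequate-power statements in sections 4.1 and 10.0 would not hold for this endpoint.

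The arithmetic rests on the two-sample *t* calculation at 11 per arm. That an arm-specific SD lies behind the 86% is an inference. The SD rule is stated for fasting acyl-ghrelin, so none of these figures describes power for the meal-test response in Hypothesis 2. I rate this as something that should be fixed, by disclosure and correction.

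**What to change.** 1. Add to Table 1 the SD of change assumed in each arm for all three rows, on one convention. SDs of 7.5 (retention) and 8.8 (VAS) in both arms reproduce the printed 96% and 80%.
2. In section 5.2, say which change the percentage refers to and whether the SD is common to both arms.
3. Restate ghrelin power as about 80% if SD 32 is meant, or about 61% if SD 40 is meant, and label the row as fasting acyl-ghrelin.
4. Only if SD 40 is meant, qualify the adequate-power statements in sections 4.1 and 10.0 for fasting acyl-ghrelin.
5. Keep a figure near 86% only if unequal SDs of about 40 (MRP) and 8 to 11 (device) are confirmed, justified and printed.

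The cost is one corrected table row and one or two sentences. No patients are added and the analysis does not change. The only downside is a less favourable stated power.

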8.0 Potential Risks for Patients

8.1 General: We anticipate no psychological, social or legal risks beyond those of participation in health-related research in general. The potential risks associated with participation in this study are small. They will be explained to all subjects who desire to participate in this research project. In addition, subjects will be informed that there is a possibility of unforeseeable risk, although we consider this unlikely. The research coordinator and/or the PI will ensure understanding of the consent and study procedures, as well as laboratory results; in addition, the research coordinator and/or PI will explain the various procedures and answer any questions the subjects may have before initiating any procedures. Whenever concerns arise, subjects will be informed that they are free to withdraw from the study at any time with no bias or prejudice.

8.2 Confidentiality: All key personnel involved in the design or conduct of the research involving the human subjects will receive the required education on the protection of human research participants prior to the start of this project. All specimens will be obtained solely for research purposes. Study samples and datasheets will be coded with an identification number for each subject. All data will be treated confidentially, and the subjects' names and identities will not be disclosed in any published reports. Clinic records are maintained in EPIC and study related data will be maintained on de-identified case report forms that will be entered into RedCap. A locked excel spreadsheet on a secured server will be used to maintain the key to the identification of study subject ID numbers.

8.3 Questionnaires: Patients could screen positive for moderate or severe depression or an eating disorder. Patients will be notified of these results and referral resources will be given to patients. If the patient wants these results sent to their primary care physicians, a copy of the results and referral resources will be sent to the subject's primary care physician.

8.4 Gastric Emptying Study: This research involves exposure to radiation equivalent to 40 mrems per study from the gastric emptying study. This is equivalent to <13%% of the amount of average radiation exposure adults in the US receive each year. Participants could also have an allergic reaction to the food components of the test. All subjects will be advised of the radiation exposure and will be questioned about food allergies and if they have a known allergy to any component of the test meal, they will be excluded from the study.

8.5 Intravenous catheter insertion: Possible side effects of intravenous catheter insertion are discomfort, bruising, and/or bleeding at the site of needle insertion. Occasionally some people experience dizziness or feel faint. An infection can occur at the site of catheter insertion. Aseptic technique for intravenous catheter insertion will be used to prevent infection, participants will have IV catheter insertion while seated or reclined, and the site will be monitored during the mixed meal test for any signs of intravenous catheter malfunction.

9.0 Data Monitoring:

This the study related procedures in this protocol (questionnaires, visual analog scale, gastric emptying study, and mixed meal tests with blood draws) are low risk. The PI will review any adverse events that occur from study related procedures as they occur. There will not be a formal interim analysis.

10.0 Potential Scientific Problems:

This is an ambitious protocol which will require enough patient volume for adequate enrollment, however we have adequate patient populations to recruit for this study. Detailed follow-up of patients is necessary to ensure testing at 10% TBWL, and I have experience with two other trials that required carefully monitoring weight to eliminate confounding from change in weight. I will employ similar strategies in this study to test patients at the required %TBWL and we have budgeted for an assumed 20% attrition rate after enrollment and baseline testing to have adequate sample to achieve sufficient

power.

11.0 Funding:

Grant funding is currently pending for this study from the American Society for Gastrointestinal Endoscopy, but PI start-up funds are currently available to complete all study testing.

References

